- (1) Net changes of the following parameters from baseline to 3 month after the treatment day: functional bladder capacity (FBC), voiding frequency at daytime and voiding frequency at night time, incontinence, as recorded in 3-day voiding diary.
- (2) Global response assessment (GRA) of satisfaction by the patient (categorized into -3, -2, -1, 0, 1, 2, 3, indicating markedly worse to markedly improved) at 3 month after the last treatment day. An improvement of GRA by 2 scales at 3 months is considered effective.
- (3) Net changes of the maximum flow rate, voided volume, Pdet@Qmax, and postvoid residual volume from baseline to 3 months after the treatment day.
- (4) Changes of Underactive Bladder Questionnaire (UAB-Q) score.
- (5) Changes of urinary nerve growth factor and cytokines level from baseline to 3 months after treatment day.

Patients who are not effective to the treatment at 3 months will receive repeated ESWT treatment.

Safety

- (1) Local adverse event incidences (hematuria, miction pain, UTI, urinary retention) are reported.
- (2) Any systemic adverse event occurring after ESWT will be asked to report and patients will be properly investigated and treated. The cause for systemic adverse event may be not related with ESWT treatment.

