5.2.9 Evaluation Visit II (V8, 12 week \pm 7 days after the V6)

5.2.9.1 Review patients voiding diary for urinary frequency, functional bladder capacity, and record reported UAB symptom score, and GRA.

5.2.9.2 Vital signs monitoring and record adverse events.

5.2.9.3 Check urinalysis for urinary tract infection if patient has symptoms suggestive of urinary tract infection.

5.2.9.4 Perform Uroflowmetry study for maximum flow rate, urodynamic study and PVR volume.

5.2.9.5 Collect 30 ml urine for analysis of the urinary NGF and cytokines levels.

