7. STATISTICAL ANALYSIS

7.1. Evaluability

Patients receiving baseline screening and treatment will be considered as intent-to-treat (ITT) population. The ITT population with the following conditions will be considered as per-protocol (PP) population:

- 1. Not taking any prohibited medications
- 2. Fulfilling all entry criteria
- 3. Have treatment visit and post-treatment evaluations on the primary endpoint

The efficacy evaluation will be performed on both the ITT and PP datasets while the safety evaluations will be performed only on the ITT datasets. The primary conclusions will be made for the primary and secondary endpoints on the ITT patients.

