7.2 Analysis

The statistical objective of this study is to demonstrate that the efficacy of ESWT is superior to placebo with respect to the decreases of UAB symptom score, and PVR. The safety profile of ESWT or placebo for the either group of treatment of patients with DU/UAB will also be confirmed.

Primary Efficacy Endpoint

The efficacy of ESWT treatment will be evaluated for:

(1) Net changes of the mean post void residual (PVR) volume (mL) from baseline to 1 month after the treatment day.

Secondary Efficacy Endpoint

The efficacy of ESWT will be evaluated for:

- (1) Net change of the following parameters from baseline to 1 month after the treatment day: functional bladder capacity (FBC), voiding frequency at daytime and voiding frequency at night time, incontinence, as record in 3-day voiding diary.
- (2) Global response assessment (GRA) of satisfaction by the patient (categorized into -3, -2, -1, 0, 1, 2, 3, indicating markedly worse to markedly improved) at 1 month after the treatment day. An improvement of GRA by 2 scales at 1 month is considered effective.
- (3) Net changes of the maximum flow rate, voided volume, Pdet@Qmax, and postvoid residual volume from baseline to 1 month after the treatment day.
- (4) Changes of Underactive Bladder Questionnaire (UAB-Q) score.
- (5) Changes of urinary nerve growth factor and cytokines level from baseline to 1 month after treatment day.

Voiding frequency at daytime and nighttime is measured as mean of the three-day voiding diary preceding the scheduled visit and the record days are 3 days.

Net change of each efficacy item will be analyzed by paired t-test between baseline and post-treatment in the treatment group and controlled group. The net changes of each efficacy item will be analyzed by ANOVA test to compare between treatment group and controlled groups. The global response assessment by the patients will be analyzed by Fisher exact test between the treatment and controlled groups.

All efficacy variables will be reported of respective point estimated and 95% confidence interval. Comparison tests will be reported of respective p value.

Secondary Safety Endpoints

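### SAP 7.2 compares Pdet@Qmax at 1 month, but the itemised visit schedule has post-treatment urodynamics only at V8, and the SAP gives the 3-month efficacy endpoints no time point or status

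*Protocol*

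**What the plan says.** Protocol section 2 has three efficacy tiers: a primary endpoint at 1 month, secondary endpoints at 1 month, and a separate 3-month follow-up. The follow-up tier has five groups: diary variables; GRA; flow, voided volume, Pdet@Qmax and PVR; UAB-Q; and urinary NGF and cytokines. Its third group is "Net changes of the maximum flow rate, voided volume, Pdet@Qmax, and postvoid residual volume from baseline to 3 months after the treatment day". GRA has its own response rule at that visit: "An improvement of GRA by 2 scales at 3 months is considered effective".

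SAP 7.2 sets the primary endpoint as "Net changes of the mean post void residual (PVR) volume (mL) from baseline to 1 month after the treatment day". Its secondary list includes "Net changes of the maximum flow rate, voided volume, Pdet@Qmax, and postvoid residual volume from baseline to 1 month after the treatment day" and, for GRA, "An improvement of GRA by 2 scales at 1 month is considered effective". UAB-Q is listed without a time point. The tests are a paired t-test within each arm, ANOVA on net change between arms, and Fisher's exact test for GRA. Neither 3 months nor V8 is named in SAP 7.1 to 7.4. On inference, SAP 7.1 says "The primary conclusions will be made for the primary and secondary endpoints on the ITT patients".

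In the visit schedule, Protocol 5.2.1 (V0) lists a urodynamic study. Protocol 5.2.8 (V7, the primary end-point visit) lists uroflowmetry for maximum flow rate, voided volume and PVR. Protocol 5.2.9 (V8) says "Perform Uroflowmetry study for maximum flow rate, urodynamic study and PVR volume". Protocol 5.1, in general terms, includes urodynamic studies among the assessments at the required visits and names the primary end-point visit as one of them.

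**The concern.** Pdet@Qmax comes from pressure-flow testing, and Protocol 4.2.8 uses it that way in the entry criteria. Uroflowmetry and PVR at V7 do not supply it. If sites follow the itemised V7 list, every patient's 1-month Pdet@Qmax is absent. SAP 7.3 treats incomplete observations as missing with no estimation, so the planned comparison would have no data. Meanwhile the V8 urodynamic study, which requires catheterisation (Protocol 4.3.13 anticipates this), would be done with no stated comparison.

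The other 3-month endpoints have a milder form of the same problem. The protocol says efficacy will be evaluated at 3 months and V8 collects the data, but the SAP does not say whether those results are secondary, supportive or exploratory, or which test applies. Whether an effect lasts, and whether detrusor pressure changes, would then be answered by choices made after the data are seen.

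**Working it through.** **1. The plan's own figure.** The only quantitative statement in the SAP concerns 1-month PVR (SAP 7.4): 24 per arm, difference -50 mL, SD 60 mL, two-sided alpha 0.05, power 80.677%.

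- Noncentrality = 50 / (60 × √(2/24)) = 50 / 17.32 = 2.887, with 24 + 24 − 2 = 46 degrees of freedom.
- Exact noncentral-t power = 80.677%, which matches.
- Enrolment = 48 / (1 − 0.20) = 60, which matches.

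The figure reproduces and applies only to 1-month PVR. The documents give no effect size or SD for any 3-month endpoint or for Pdet@Qmax, so no power can be computed for those. The rest is a comparison of text.

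**2. Where urodynamics are itemised (Protocol 5.2).**

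| Visit | Timing | Urodynamic study | PVR |
|---|---|---|---|
| V0 | 2 weeks before treatment | listed | listed |
| V1 to V6 | weekly treatments | not listed | not listed |
| V7 | 4 weeks after V6 | not listed | listed |
| V8 | 12 weeks after V6 | listed | listed |

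A change from baseline in Pdet@Qmax needs two urodynamic studies. The itemised schedule supports V0 to V8 and does not support V0 to V7.

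**3. Where Pdet@Qmax is to be analysed.**

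| Source | 1 month | 3 months |
|---|---|---|
| Protocol 2, secondary endpoints | yes | – |
| Protocol 2, follow-up | – | yes |
| SAP 7.2 | yes | not mentioned |

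Putting the two tables together: the change the SAP tests (V0 to V7) has no itemised measurement, and the change the schedule measures (V0 to V8) has no place in the SAP.

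**4. Status of the remaining 3-month endpoints.** The protocol's follow-up tier has five groups. In SAP 7.2 each counterpart is dated 1 month, except UAB-Q, which is undated. The tier is labelled neither primary nor secondary, and SAP 7.1 draws its conclusions from primary and secondary endpoints. The methods could be carried over to V8, because the ANOVA sentence covers every efficacy item and the paired test uses an undated post-treatment value. Those sentences follow a 1-month list, however, so the extension is possible without being stated.

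**The case against.** The best defence has three parts.

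- **The methods already reach V8.** The generic test wording lets the same ANOVA be run once per visit, and Fisher's exact test applies to GRA at V8 in the same way. This stands in part: a usable method exists, and what is missing is the time point and the status. A reader might infer that the 3-month data have no possible analysis; the wording does not support going that far.
- **The follow-up tier has a role.** Its separate heading reads naturally as a supportive tier, and the protocol uses the 3-month result: "Patients who are not effective to the treatment at 3 months will receive repeated ESWT treatment". That stands against any claim that the data serve no purpose. The use is patient management, however, and it does not tell the statistician what to test.
- **Urodynamics may be intended at V7.** Protocol 5.1 points that way, and the V7 list could simply have omitted them. This also stands, and it rules out asserting that no 1-month Pdet@Qmax data will exist. What it shows is a contradiction between Protocol 5.1 and Protocol 5.2.8, which should be settled before analysis.

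Two stronger readings are tempting. A reader might infer that a positive 3-month PVR result could replace a null 1-month one, and might compute an inflated error rate for two PVR tests. The primary endpoint is fixed at 1 month in Protocol 2, SAP 7.2 and SAP 7.4. An inflated rate would need a rule that success at either visit counts, plus an assumed correlation between visits, and the plan contains neither. A reader might also conclude that a repeated-measures mixed model is required. That would replace the analysis planned and powered for the primary endpoint and change the missing-data approach in SAP 7.3, and the gap can be closed without it.

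**Conclusion.** The concern holds in a limited form. On the itemised schedule, SAP 7.2 places one secondary endpoint, Pdet@Qmax, at a visit with no listed measurement, and it omits the visit where the measurement is listed. The other 3-month efficacy endpoints lack a stated time point and status in the SAP; for these alone the gap would be missing detail. The Pdet@Qmax mismatch makes a specific change worthwhile.

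This rests on reading the visit lists in Protocol 5.2 as governing what is done at each visit. If Protocol 5.1 governs and urodynamics are performed at V7, the 1-month endpoint can be analysed and the fault is in the V7 list; the V8 results would still have no status. No numerical bias or error rate follows from the documents. The primary PVR comparison, its 80.677% power and the sample size of 60 are not affected.

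**What to change.** 1. Reconcile Protocol 2, 5.1, 5.2.8 and 5.2.9 with SAP 7.2 on when urodynamics are performed and when Pdet@Qmax is analysed. The V8 window needs the same attention: it is ±3 days in 5.2.8.5 and ±7 days in 5.2.9.
2. In SAP 7.2, move the between-arm comparison of change in Pdet@Qmax to V8 (3 months), where the measurement is scheduled.
3. Add a statement that the planned ANOVA, and Fisher's exact test for GRA, are also applied at V8 to the 3-month endpoints in Protocol 2, as supportive analyses.
4. State that the 1-month PVR comparison is the sole primary test and that no 3-month result can replace it.

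The cost is a few sentences in the SAP and matching edits to the protocol, with no new visits, data or patients. There are two downsides: Pdet@Qmax becomes a 3-month rather than a 1-month endpoint, and 3-month results cannot rescue a null primary result.

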3. SHOCK WAVE MACHINE AND PROCEDURES

The shock wave applicator, FS-I (“LITEMED” LM-ESWT-mini system, Taiwan), will be gently placed on the skin area over the bladder dome, right upper lateral wall, right lower lateral wall, left upper lateral wall, and left lower lateral wall during once a week for 6 weeks, with 2500 shocks, frequency of 4 pulses per second, and maximum total energy flow density 0.25 mJ/mm². The current shock wave intensity and number used was followed from reference [1].

Eligible patients will be assigned a randomization number in sequential order and each of the randomization will determine the allocation of one of the two treatment groups (ESWT and Placebo) in 1: 1 ratio as shown below. The ESWT and placebo will be controlled by a research assistance who will not evaluate the therapeutic outcome to ensure the double-blind method.

Vital signs (body temperature, blood pressure, heart rate and respiration rate) will be recorded at pre-treatment and 30 minutes following treatment.

The treatment will be carried out in the out-patient clinic. Patient will be stayed in a treatment room and accompanied by a research assistant.

3.1. Randomization

Permuted block randomization method will be applied to generate randomization codes. Each randomization number will be assigned to individual patient according to the time-sequence for screened patient become eligible.

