4.2. Inclusion Criteria

Patients must meet all the following criteria to be eligible to enter the trial:

- 4.2.1. Adult male or female, at least 20 years of age.
- 4.2.2. History of UAB (defined as bothersome chronic incomplete bladder emptying) for at least 3 months documented in the medical record with recurring UAB symptoms.
- 4.2.3. No UAB symptom relief (unresponsiveness) with previous used medications and/or other treatments.
- 4.2.4. Voiding difficulty (complains of difficulty emptying the bladder).
- 4.2.5. UAB consistent with diabetes, MS, Parkinson's disease, or aging idiopathic.
- 4.2.6. Post void residual ≥ 100 mL.
- 4.2.7. Bladder capacity > 200 mL and < 800 mL.
- 4.2.8. Pressure flow Urodynamic testing demonstrating impaired detrusor contractility or areflexia without evidence of BOO, with maximum detrusor pressure Pdet at Qmax (Pdet@Qmax) of < 20 cmH₂O and Maximum flow rate (Qmax) < 15 mL/sec for female and BCI <100 and BOOI < 40 for male [2, 3].
- 4.2.9. Total UAB Questionnaire Score ≥ 3 .
- 4.2.10. Females of child-bearing potential agree to use reliable birth control for the entire study duration.
- 4.2.11. Willing and capable of understanding and complying with all requirements of the protocol, including proper completion of the voiding diaries and self-administered questionnaires.
- 4.2.12. Free of active urinary tract infection.
- 4.2.13. Free of bladder outlet obstruction on enrollment.
- 4.2.14. Patient or his/her legally acceptable representative has signed the written informed consent form.
- 4.2.15. Subject on clean intermittent catheterization (CIC) should have been on CIC for at least 1 month and should be able to void spontaneously and not be completely dependent on CIC.

4.3.Exclusion Criteria

- 4.3.1. Female patients who is pregnant, lactating, plans to become pregnant, or with child-bearing potential without contraception.
- 4.3.2. Simultaneously participating in another investigational drug or device study or use of any investigational drug(s) or therapeutic device(s) within 3 months preceding enrollment.
- 4.3.3. Has been treated with an investigational device, drug, or procedure for UAB within the last 3 months.
- 4.3.4. History of cancer in pelvic organs, ureters, or kidneys or any cancer that has undergone treatment within the past 12 months.

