- (1) Local adverse event incidences (hematuria, micturition pain, UTI, urinary retention) will be reported by both treatment group and controlled group and by physiological systems as appropriate. Incidence of adverse events and the categories of adverse event severity between treatments will be analyzed. The coding system used will be COSTART.
- (2) The abnormalities of laboratory test results will be reported by patient list in the patients who have been tested for having severe adverse event.
- (3) The changes in physical examinations will be presented in the by-patient list.
- (4) All statistical tests used will be two-tailed with α = 0.05.

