7.4 Sample Size

We used PASS 14 to calculate power for this study. Group sample sizes of 24 and 24 achieve 80.677% power to reject the null hypothesis of equal means when the population mean difference (Net changes of the mean post void residual (PVR) volume (mL) from baseline to 1 month after the treatment day) is -50.0 with a standard deviation for both groups of 60.0 and with a significance level (alpha) of 0.050 using a two-sided two-sample equal-variance t-test. According to 20% of the patient's drop-out rate, the number of subjects is set to 60, and the evaluator is 48 to get enough verification power.

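### Sex sets the urodynamic entry limits but is used in neither the randomisation nor the between-arm model: a minor loss of precision, not a bias

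*Protocol*

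**What the plan says.** Both sexes may enter and no quota is set (Protocol 4.2.1). The urodynamic criterion in 4.2.8 then separates them: "Qmax) < 15 mL/sec for female and BCI <100 and BOOI < 40 for male". The sentence does not make clear whether the Pdet@Qmax limit that precedes these words applies to women only, but the criteria differ by sex on either reading. The PVR limit (4.2.6) and the bladder capacity limits (4.2.7) are common to both sexes.

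On allocation, Protocol 3.1 states: "Permuted block randomization method will be applied to generate randomization codes". Numbers are given out in the order in which patients become eligible, and no stratum is named. That there is one unstratified list is inferred from this silence and from the time-ordered assignment.

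On analysis, SAP 7.2 states: "The net changes of each efficacy item will be analyzed by ANOVA test to compare between treatment group and controlled groups". No covariate or second factor is named. The GRA comparison is an unstratified Fisher exact test. SAP 7.4 sizes the trial on an unadjusted comparison, with a "significance level (alpha) of 0.050 using a two-sided two-sample equal-variance t-test".

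**The concern.** Sex is known before randomisation, and the protocol itself treats it as relevant to how the disease is defined. With about 24 evaluable patients per arm, an unstratified list can leave the arms visibly unequal in sex. If men and women, admitted under different definitions, also differ in how much their outcomes change, part of the observed arm difference in such a trial would reflect sex mix. The plan has no prespecified means of correcting for this. An adjustment chosen after seeing the imbalance would be post hoc and open to challenge. What is at stake is some precision, and the credibility of the result in the particular trial that turns out unbalanced.

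**Working it through.** **Inputs from the documents.** SAP 7.4: 24 per group, planned difference −50 mL, SD 60 mL, dropout 20%, 60 enrolled. SAP 7.2: two-sided α = 0.05. Protocol section 3: 1:1 allocation.

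**Assumptions (not in the documents).** Share of women 30% to 50%. Male-female gap in mean PVR change: 0, 30 or 60 mL. The SD of 60 is read as the total SD, so it already contains any variation between the sexes.

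**1. The plan's own figure.** SE of the arm difference = 60 × √(2/24) = 17.32 mL. Noncentrality = 50 / 17.32 = 2.887. Noncentral t with 46 df, two-sided 0.05, gives power 80.68%, matching the stated 80.677%. Enrolment: 48 / (1 − 0.20) = 60, as stated.

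**2. Chance of a sex imbalance.** With the number of women in each arm taken as an independent binomial (n = 24), P(difference of at least 5 women) is:

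| Share of women | Probability |
|---|---|
| 50% | 19.3% |
| 40% | 18.4% |
| 30% | 15.5% |

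Five of 24 is 20.8 percentage points. As a cross-check, fix the minority sex at 24, 16 or 12 of the 48 (hypergeometric). An even total allows only even differences, so the relevant event is at least 6 of 24 (25 points). Its probability is 14.8%, 12.5% or 9.3%.

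**3. Shift in the PVR difference.** Shift = imbalance × sex gap in change.
- Gap 0: 0 mL.
- Gap 30 mL: 5/24 × 30 = 6.25 mL, or 0.36 SE.
- Gap 60 mL: 5/24 × 60 = 12.5 mL, or 0.72 SE.

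**4. Is the unadjusted test biased?** In 40,000 simulated trials per gap (blocks of 4 assumed, half women, 24 per arm, total SD 60), the mean error in the arm difference was about 0. Type I error was 4.9% at a 30 mL gap and 5.0% at 60 mL. By realised imbalance:

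| Imbalance | Type I error, gap 30 mL | Type I error, gap 60 mL |
|---|---|---|
| 0 points | 3.7% | 2.3% |
| 12.5 points | 4.4% | 4.2% |
| 25 points | 6.3% | 8.9% |

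The overall level is therefore held, and the departures in unbalanced and balanced trials offset each other.

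**5. Power with sex in the model** (half women). Residual SD = √(3600 − 0.25 × gap²), 45 df. A 25-point imbalance multiplies the noncentrality by √(1 − 0.25²) = √0.9375.

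| Gap (mL) | Residual SD | Power, sex balanced | Power, 25-point imbalance |
|---|---|---|---|
| 0 | 60.00 | 80.64% | 78.1% |
| 30 | 58.09 | 83.1% | 80.6% |
| 60 | 51.96 | 90.3% | 88.5% |

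If sex is irrelevant and only the model term is added, averaging over the binomial imbalances gives 79.8%, a loss of about 0.9 points. At a 25-point imbalance the loss is 80.7 − 78.1 = 2.6 points. These figures are for the sex term only; the effect of also adding the baseline value was not computed, because the documents give no correlation between baseline and change.

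**The case against.** A simple permuted-block list with an unadjusted comparison is a legitimate design for 60 patients at one centre. Several of the opposing points stand in full.

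- **A reader might infer that a sex imbalance passes directly into the results.** It does not. The endpoints are changes from baseline, so a constant male-female difference in level cancels. Sex must predict the change, and the documents offer no evidence either way.
- **A reader might infer that the different entry limits show a sex effect on the primary endpoint.** They do not. They concern urodynamic measures, and the PVR limit is shared.
- **A reader might infer a large built-in contrast in Pdet@Qmax at 1 month.** The documents do not support this. The sentence in 4.2.8 is ambiguous about whom the Pdet@Qmax limit covers, and the 1-month visit (V7, 5.2.8) lists uroflowmetry and PVR but no urodynamic study. Urodynamics are listed at screening and at V8, so as scheduled the question arises only at 3 months.
- **The noise is already budgeted.** If 60 mL is the total SD, sex-related variation is inside the 80.7%. The upper assumed gap of 60 mL is a full SD and exceeds the planned treatment effect, so it is an outer bound.
- **Other baseline factors have a claim.** Cause of disease and catheter use could be unbalanced too, and baseline PVR is the more direct covariate for PVR change.

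What remains is narrow: sex is the one characteristic by which the protocol itself splits the diagnostic criterion, and using it costs almost nothing if the blocks are stratified. The last objection is a reason to include the baseline value alongside sex, not to leave both out.

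**Conclusion.** The point holds as a minor, inexpensive improvement in precision. Entry limits differ by sex, no stratification by sex is stated, and no planned comparison includes sex. An imbalance of at least 5 of 24 has about a 15% to 19% chance. Its effect on the PVR difference is 0 mL if sex does not predict change, and 6 to 13 mL at an assumed gap of 30 to 60 mL. The likely gain in power is modest, about 2.4 points at a 30 mL gap with sex balanced.

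This does not invalidate the primary analysis or call for a change in sample size. The shifts, the conditional error rates and the gains in power all rest on the assumed sex mix and sex gap, neither of which the documents give.

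**What to change.** If randomisation has not begun, amend Protocol 3.1 to: *permuted-block randomisation, 1:1, stratified by sex (two lists)*. In SAP 7.2, prespecify sex as a factor, together with the baseline value of the outcome, in the between-arm model for the change endpoints. If randomisation has begun, keep the existing list and make only the 7.2 change, dated before unblinding.

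**Cost.** One further computer-generated list at a single centre, and one degree of freedom for sex plus one for the baseline value. No added patients, visits or staff, and enrolment stays at 60.

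**Downsides.** Two incomplete final blocks may leave the arms unequal by a few patients overall. Without stratification, the sex term costs about 1 point of power on average if sex turns out to be irrelevant, and 2.6 points at a 25-point imbalance.
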